4.1 Duration of Participation

Twelve weeks

4.2 Primary Study Endpoints

The primary endpoint of the study will be the mean UAS7 reduction before and after 10 weeks of treatment with mepolizumab. The urticaria activity score (UAS) is a widely used CSU measure for daily pruritus and number of hives, which summed over a week, gives a UAS7 score. Study participants will document their CSU symptoms using a diary during the 10 week study period using the following daily scoring for a) the number of wheals [none (=0 points), <10 (=1 point), 10–50 (=2 points), or >50 per day (=3 points)], and b) the intensity of pruritus [none (=0 points), mild (=1 point), moderate (=2 points), severe (=3 points)]. The daily UAS score is summed over a week to calculate the UAS7 score (range: 0–42).

4.3 Secondary Study Endpoints

The secondary endpoints of the study are the mean reduction in the weekly itch severity score (ISS) and mean average change in the urticaria control test (UCT) score before and after 10 weeks of treatment with mepolizumab. The weekly itch severity score is calculated using the pruritus score of the daily UAS score summed over a week (range: 0–21). The urticaria control test (UCT) is a more recently developed and validated outcome instrument to retrospectively assess urticaria

control. Each UCT item has 5 answer options scored 0-4 with low points indicating high disease activity and low disease control. The minimum and maximum UCT scores are 0-16 with 16 points indicating complete disease control.

4.4 Primary Safety Endpoints

This is an exploratory efficacy study with no specific primary safety endpoint. Adverse events will be tracked and reported using Good Clinical Practice standards.

4.5 Identification of Source Data

The following source data will be directly recorded on the Case Report Form (CRF):

- UCT score
- ISS score
- UAS7 score
- Screening and documentation of adverse events
- Confirmation of patient counseling and education

The following source data will not be directly recorded in the CRF, but will be captured in supportive documentation to include study source documents and the EMR:

- Laboratory results and clinical interpretation of the values
- Histopathologic interpretations of skin biopsy tissue. This will include the use of immunohistochemistry to identify IL-5 receptor expression in lesional skin taken prior to treatment.

5 Subject Selection Enrollment and Withdrawal

5.1 Inclusion Criteria

Informed subject consent will be obtained from those patients meeting the following inclusion criteria:

- Male and female patients 18 years or older.
- Clinical and/or histopathological diagnosis of conventional CSU
- Unresponsive to oral antihistamine therapy
- Good general health as confirmed by medical history
- Patients who are willing and capable of cooperating to the extent and degree required by the protocol; and
- Patients who read and sign an approved informed consent for this study

5.2 Exclusion Criteria

Patients are to be excluded based on the following criteria:

- Vulnerable study population
- If you are female and pregnant
- Biopsy proven neutrophilic rich urticarial which is unlikely to respond to mepolizumab given the postulated therapeutic mechanism
- Known history of adverse reaction to mepolizumab (Nucala)

5.3 Subject Recruitment, Enrollment and Screening

Subjects will be enrolled from the Departments of Allergy and Dermatology at the Mayo Clinic in Florida. The study has an accrual target of 20 patients. In the year 2014, 188 unique patients with CSU were evaluated in the Dermatology and Allergy outpatient clinics at Mayo Clinic in Florida and thus no difficulties in accrual based on historical volumes are anticipated. Co-departmental participation aids in reaching accrual targets and minimizing referral bias. The accrual period will last 10 months. Patients will be provided with a Research Participant Consent and Privacy Authorization Form describing the study drug, protocol, inclusion and exclusion criteria, as well as risks and benefits of participation.

5.4 Early Withdrawal of Subjects

5.4.1 When and How to Withdraw Subjects

Patients are free to withdraw at any time and for whatever reason. No data will be collected for withdrawn subjects. Withdrawn subjects may be replaced within the 6-month accrual period. There will be no follow-up for withdrawn subjects. Pre-specified reasons for discontinuing include, but are not limited to, the following:

- Patient Request: Patient decided that he/she did not want to continue (for any reason)
- Adverse Event: Patient experienced a related or unrelated event that would interfere with the study objectives/evaluation
- Lost to Follow-up: Patient did not come in for a visit and could not be reached by phone
- Treatment Failure: If in the Principal Investigator and/or Investigators' judgment, the patient's condition required another form of treatment
- Inclusion/Exclusion Discrepancy/Violation: Patient should not have been enrolled
- Noncompliance: Patient is not complying with the protocol requirements (i.e. visit schedule, dosing, regimen, etc.); a patient is to be withdrawn if he/she misses two consecutive visits
- Other: Any other reason

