5.4.2 Data Collection and Follow-up for Withdrawn Subjects

If a Participant withdraws from the study, no additional attempts will be made to contact the Participant.

6 Study Drug

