8.1 Sample Size Determination

The statistical methods proposed in the study were reviewed with a Mayo staff statistician who also assisted in a formal power analysis. Demographic and laboratory characteristics will be analyzed using descriptive statistics. A paired t-test will be used to evaluate mean differences before and after treatment at a $p=0.05$ significance level. The primary endpoint of the study is the UAS7. A 10 point change in the UAS7 has been reported to be the minimal clinically significant difference in therapeutic trials for urticaria. The study is powered at 99% to detect a 10 point change in the UAS7 at a 5% significant level with the proposed accrual target of 20 patients.

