8.2 Statistical Methods

Descriptive Statistics

Continuous variables will be summarized using the sample mean, median, standard deviation, interquartile range, and range. Categorical variables will be summarized using number and percentage of patients

Handling of Missing Data

This is a prospective study and therefore we do not anticipate any missing data. In the event of any unexpected missing data, no attempt to impute this missing data will be made; missing data will simply be treated as missing in the statistical analysis.

Multiplicity

Since this is an exploratory pilot study, no adjustment for multiple testing is needed.

Interim Analysis

There will not be any interim analysis given the low risk profile of the study formulation.

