8.3 Subject Population(s) for Analysis

Each participant who received the study drug will be included in the primary analysis regardless of study withdrawal for any reason. In the event of any study withdrawals, in secondary analysis we will examine the sensitivity of our results to the exclusion of patients who withdrew.

9 Safety and Adverse Events

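### Section 8.3 promises to analyse every dosed subject, but those who withdraw without a week-10 UAS7 cannot enter the paired test, and for them the exclude-withdrawals check only repeats the primary result

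*Combined protocol and SAP*

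**What the plan says.** - **Population (Section 8.3).** "Each participant who received the study drug will be included in the primary analysis regardless of study withdrawal for any reason". If there are withdrawals, "in secondary analysis we will examine the sensitivity of our results to the exclusion of patients who withdrew".
- **Endpoint (Section 4.2).** "The primary endpoint of the study will be the mean UAS7 reduction before and after 10 weeks of treatment with mepolizumab".
- **Test (Section 8.1).** "A paired t-test will be used to evaluate mean differences before and after treatment", at the 5% level, with 20 subjects and a claimed 99% power for a 10-point change.
- **Data after withdrawal (Sections 5.4.1 and 5.4.2).** "No data will be collected for withdrawn subjects. Withdrawn subjects may be replaced within the 6-month accrual period", and "If a Participant withdraws from the study, no additional attempts will be made to contact the Participant".
- **Missing data (Section 8.2).** "This is a prospective study and therefore we do not anticipate any missing data". Should any occur, it is not imputed: "missing data will simply be treated as missing in the statistical analysis".

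Section 5.4.1 lists seven categories of withdrawal reason. One is treatment failure as judged by the investigators. Section 10.3 requires missing data to be explained, so reasons should be on record, but no planned analysis uses them.

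**The concern.** The rules in Sections 8.3, 8.2, 8.1 and 5.4 cannot all be followed for a subject who is dosed and then withdraws without a week-10 score. Section 8.3 says the subject is in the primary analysis; the other three leave no week-10 value to analyse. A report could then describe an all-dosed primary analysis, supported by a sensitivity analysis that agrees with it, when the agreement is automatic.

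This matters because the study has no control arm: the mean within-subject change is the efficacy result. Subjects withdrawn for treatment failure would tend to be those who responded least, and they may be replaced. The mean among those who remain could then overstate the benefit, and the only planned check would not reveal it.

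**Working it through.** **Step 1. Who contributes to each analysis.** The paired t-test uses d = UAS7(week 0) − UAS7(week 10), so a subject contributes only with both scores. Suppose 20 are dosed, k withdraw without a week-10 score, and nobody is replaced.

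- Primary analysis (all dosed, no imputation): 20 − k differences.
- Exclude-withdrawals analysis: the same 20 − k differences.

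Estimate, standard error and p-value are therefore identical. A simulated data set with k = 4 gave n = 16 and t = −1.974 in both (there coded as week 10 minus week 0). A subject who stays in the study but lacks week 10 drops out of both analyses as well. The two differ only if someone is classed as withdrawn after giving a week-10 score.

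**Step 2. The plan's power figure.** No SD is stated, so the 99% cannot be reproduced directly. Solving the two-sided 5% paired t-test for the SD that gives it: noncentrality = 10 × √20 / SD, 19 degrees of freedom, critical value 2.093. Power is 99.0% at SD = 9.88 (noncentrality 4.52). This implied SD is used below as an assumption. At n = 16 the same SD gives 96.5%, so lost power is not the issue.

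**Step 3. Illustrative bias.** Assumptions, none of them from the documents: true change 0; normal, unbounded changes; no replacement; the k subjects ranked lowest on a variable having correlation ρ with week-10 improvement withdraw. Then

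mean inflation = ρ × SD × a(k),

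where a(k) is the expected mean of the top 20 − k of 20 standard normal values: 0.098, 0.182 and 0.333 for k = 1, 2 and 4. For k = 4 and ρ = 0.5: 0.5 × 9.88 × 0.333 = 1.6. The chance of a significant improvement comes from simulation (200,000 runs per setting).

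| Withdrawn of 20 | Inflation (points), ρ = 0.2 to 0.5 | P(significant improvement), nominal 2.5% |
|---|---|---|
| 1 | 0.2 to 0.5 | about 3 to 4% |
| 2 | 0.4 to 0.9 | about 3.5 to 6% |
| 4 | 0.7 to 1.6 | about 4.4 to 10% |

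At ρ = 0 there is no inflation and the chance is 2.5%. With negative ρ (improved subjects leave) the bias reverses.

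**Step 4. Would a tipping-point analysis be informative?** Take 16 subjects with both scores, mean reduction m and SD s = 9.88, and 4 without week 10, each assigned a worsening of w points.

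M = (16m − 4w)/20

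S² = [15s² + 16(m − M)² + 4(w + M)²]/19

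t = M/(S/√20)

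- m = 10: primary t = 10/(9.88/4) = 4.05, p = 0.001. With w = 0, M = 8.0, S = 9.69, t = 3.69, p = 0.002. Significance is lost only at w of about 11.1 (M = 5.77, S = 12.34, t = 2.09).
- m = 6: primary t = 2.43, p = 0.028. With w = 0, M = 4.8, S = 9.12, t = 2.35, p about 0.03. Significance is lost at w of about 2.

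The analysis separates a robust result from a fragile one. Excluding withdrawals just returns p = 0.001 and p = 0.028 again. Zero change alone is not enough: it lowers the mean by 20% but hardly moves the test. Under Step 3 with k = 4 and ρ = 0.5, the false-positive chance stays near 10% with zeros and falls to 2.1% with 5 points of worsening.

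**The case against.** **The check is not always empty.** A reader might infer that the exclude-withdrawals analysis must always repeat the primary. It need not. Section 5.4.1 also lists eligibility violations, which may come to light after week 10; such a subject has a pair and would make the two analyses differ. That stands, and the point is limited to withdrawals without a week-10 score.

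**Earlier scores are not discarded.** Section 5.4.1 could be read as throwing away everything from a withdrawn subject. The more natural reading is that collection stops at withdrawal. UAS7 scores are recorded on the case report form (Section 4.5), and Section 10.1 allows use of information gathered before authorization is revoked. But no rule brings earlier scores into the week-10 test, and carrying one forward would be imputation, which Section 8.2 bars.

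**The harm is conditional and may be small.** This also stands. An inflation of 0.2 to 1.6 points is modest against the 10-point change the plan calls clinically significant. At a 10-point result with four withdrawals, all four would have to worsen by about 11 points to overturn the conclusion. The illustration omits the permitted replacement and the 0 to 42 range. If exactly the four poorest responders left, the chance of a false improvement would be about 38%, but nothing in the documents supports that pattern as a forecast.

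**It is an exploratory study of 20.** This limits how much machinery is proportionate. It does not excuse a stated population rule that the stated test cannot follow.

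**Conclusion.** Wrong as written, and it should be fixed. For dosed subjects who withdraw without a week-10 UAS7, the Section 8.3 inclusion rule cannot be carried out and the planned sensitivity analysis adds nothing. This follows from the text alone and needs no assumption about SD or withdrawal rate.

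The bias is a possibility, not a finding. A reader might infer that the trial will overstate benefit. The documents do not support that: several listed reasons need not relate to response, and the bias is zero if withdrawal is unrelated to it. What the documents do support is that treatment failure is a route out of the study, that replacement is allowed, and that no planned analysis would show the resulting bias. The sizes in the working depend on its assumptions throughout.

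**What to change.** 1. **Section 8.3, analysis set.** Describe the paired t-test as an analysis of subjects with both week-0 and week-10 UAS7. Report all dosed subjects, with the number withdrawn and the reasons. State that a replacement is added to the dosed set and does not substitute for the subject who left.
2. **Section 8.3, sensitivity analysis.** Replace the exclude-withdrawals analysis with one covering every dosed subject without a week-10 score, whatever the reason. Start from zero change, then assign progressively worse changes until the conclusion changes or the cap is reached. Cap each assigned UAS7 within 0 to 42; an 11-point worsening, for example, is possible only from a baseline of 31 or less (42 − 11). Amend the no-imputation sentence in Section 8.2 to allow this.

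Optional: a repeated-measures model on the UAS7 scores already scheduled, presented as reducing rather than removing bias, since it removes it only if withdrawal depends on scores already observed. If used, first reconcile Section 3.1 (UAS7 at weeks 0, 4, 8 and 10) with the Section 7 visit lists (every visit from week 0).

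Cost: some protocol wording, one sensitivity table and possibly a less favourable estimate. No new patients, visits or procedures.

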For this study, the study treatment follow-up period is defined as the last scheduled visit.

Preexisting Condition

A preexisting condition is one that is present at the start of the study. A preexisting condition will be recorded as an adverse event if the frequency, intensity, or the character of the condition worsens during the study period.

General Physical Examination Findings

At screening, any clinically significant abnormality should be recorded as a preexisting condition. At the end of the study, any new clinically significant findings/abnormalities that meet the definition of an adverse event will also be recorded and documented as an adverse event.

Post-study Adverse Event

All unresolved adverse events should be followed by the sponsor-investigator until the events are resolved, the subject is lost to follow-up, or the adverse event is otherwise explained. At the last scheduled visit, the sponsor-investigator should instruct each subject to report, to the sponsor-investigator, any subsequent event(s) that the subject, or the subject's personal physician, believes might reasonably be related to participation in this study.

Abnormal Laboratory Values

Any clinical laboratory abnormality that can reasonably be related to the administration of Nucala should be documented as an adverse event.

Hospitalization, Prolonged Hospitalization or Surgery

Hospitalization, prolonged hospitalization, or surgery is to be reported as an adverse event if it can reasonably be related to use of Nucala.

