9.2 Recording of Adverse Events

At each contact with the subject, the study team will seek information on adverse events by specific questioning and, as appropriate, by examination. Information on all adverse events should be

recorded immediately in the source document, and also in the appropriate adverse event section of the case report form (CRF). All clearly related signs, symptoms, and abnormal diagnostic, laboratory or procedure results will be recorded in the source document.

All adverse events occurring during the study period will be recorded. The clinical course of each event should be followed until resolution, stabilization, or until it has been ultimately determined that the study treatment or participation is not the probable cause. Serious adverse events that are still ongoing at the end of the study period must be followed up, to determine the final outcome. Any serious adverse event that occurs during the Adverse Event Reporting Period and is considered to be at least possibly related to the study treatment or study participation should be recorded and reported immediately.

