10.1 Confidentiality

Information about study subjects will be kept confidential and managed according to the requirements of the Health Insurance Portability and Accountability Act of 1996 (HIPAA). Those regulations require a signed subject authorization informing the subject of the following:

- What protected health information (PHI) will be collected from subjects in this study
- Who will have access to that information and why
- Who will use or disclose that information
- The rights of a research subject to revoke their authorization for use of their PHI

In the event that a subject revokes authorization to collect or use PHI, the Principal Investigator and Investigators, by regulation, retain the ability to use all information collected prior to the revocation of subject authorization. For subjects that have revoked authorization to collect or use PHI, attempts will be made to obtain permission to collect at least vital status (long term survival status that the subject is alive) at the end of their scheduled study period.

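### Sections 5.4.1 and 5.4.2 bar data collection, follow-up and contact after withdrawal, while 9.1 and 9.2 call for open adverse events to be followed; the plan does not say which prevails

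*Combined protocol and SAP*

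**What the plan says.** **Withdrawal rules.** Section 5.4.1 says "No data will be collected for withdrawn subjects" and "There will be no follow-up for withdrawn subjects". The list of reasons for discontinuing that follows includes "Adverse Event: Patient experienced a related or unrelated event that would interfere with the study objectives/evaluation". Section 5.4.2 reads: "If a Participant withdraws from the study, no additional attempts will be made to contact the Participant".

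**Safety rules.** Section 9.1, under its Post-study Adverse Event paragraph, says "All unresolved adverse events should be followed by the sponsor-investigator until the events are resolved". It also accepts two other end points: loss to follow-up, or another explanation for the event. Section 9.2 asks for the course of each event to be followed until it resolves, stabilizes, or is judged not to have been probably caused by the study. For serious events it is stricter: "Serious adverse events that are still ongoing at the end of the study period must be followed up, to determine the final outcome".

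Section 5.4 makes no exception for safety, and 9.1 and 9.2 make none for withdrawn subjects.

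**The concern.** The two sets of rules meet in one kind of subject: someone who has been dosed, is withdrawn, and has an adverse event still open at that time. Section 5.4.1 foresees this subject by listing an adverse event as a reason to discontinue. Staff who apply 5.4 stop collecting data and do not call. Staff who apply 9.1 and 9.2 keep following the event. Either way they depart from a written section.

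Section 1.6 names hypersensitivity reactions, including anaphylaxis, and herpes zoster as risks. An event of either kind could lead to withdrawal, and could still be unresolved at that point. The trial has no control arm (6.3), and the Principal Investigator oversees safety by assessing adverse events (9.6). Section 1.5 says a different regimen would be considered if significant safety concerns arose. How events ended is part of the information for that judgement, and under 5.4 it may go uncollected in subjects who left because of an event.

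**Working it through.** No arithmetic applies: the point depends on no sample size, rate or error level, and the plan states no figure to reproduce. The check compares the texts for a dosed subject withdrawn with an unresolved event.

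| Question | 5.4.1 and 5.4.2 | 9.1 and 9.2 |
|---|---|---|
| Are further data collected? | No | Yes, on the course of the event |
| Is the subject followed? | No | Yes, to one of the stated end points |
| Is contact attempted? | No | Implied, since an outcome cannot normally be learned without it |
| Strength of wording | Flat statements | Advisory for events in general, mandatory for ongoing serious events |
| Exception for the other case? | None for safety | None for withdrawal |

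Four ways of reconciling the texts were tried.

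1. *Treat the subject as lost to follow-up, which ends the duty in 9.1.* This fails. Section 5.4.1 lists loss to follow-up as a separate reason, defined by a missed visit and failure to reach the patient by phone. A subject whom staff are told not to call has not been found unreachable.
2. *Read 5.4.2 as covering only withdrawal at the subject's own initiative.* Its wording could bear that, but the no-data and no-follow-up sentences in 5.4.1 apply to all withdrawn subjects and stand directly above the list that includes adverse events.
3. *Read the duty on serious events as applying only at the end of the study period.* If a withdrawn subject's study period ends at withdrawal, a serious event open then must be followed. If it ends at the scheduled week 10 visit, a serious event still open then must be followed. Section 5.4 bars both.
4. *Let 9.3 decide.* Section 9.3 has the sponsor-investigator determine what follow-up an identified event needs. It does not mention withdrawal and does not override 5.4.

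Next, what would be lost. Section 9.2 has events recorded immediately, and 9.3 has the adverse event worksheet and log completed once an event is identified. The triggering event, and any intervention given before withdrawal, should therefore already be on record. Of the items listed in 9.3.1, those exposed are the resolution and the date of resolution. Beyond that form, the later course of the event and any new event after withdrawal are exposed. Section 9.2 has all events in the study period recorded, but 5.4 removes the means of learning of them in a withdrawn subject.

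**The case against.** The best defence is that the conflict is narrow and that ordinary practice would resolve it. The triggering event is documented before the subject leaves, 9.3 gives the sponsor-investigator discretion over follow-up, and most of the wording in 9.1 and 9.2 is advisory and allows end points other than resolution. All of this stands and limits the consequences. It does not remove the conflict: the rule for ongoing serious events is mandatory, and relying on good practice means relying on staff to set aside 5.4.1 and 5.4.2.

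A reader might infer more than the documents support:

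- *That withdrawn subjects have no safety observation after their last dose, while completers have the two weeks from week 8 to week 10.* This mixes time since withdrawal with time since last dose. Visits are two weeks apart, so a subject withdrawn at a visit before that day's injection is also nominally two weeks past the previous dose.
- *That a given share of exposed patients would lack safety outcomes.* There is no withdrawal rate to work from. Replacement is allowed, which changes the number exposed, and some withdrawals may come before dosing or with no event open.
- *That the stopping rule in 9.5 would miss flares leading to withdrawal for treatment failure.* The investigator has seen and judged such a flare before withdrawal, so it can be counted.
- *That the adverse event form would be blank for these subjects.* Most items can be completed at the time of the event.
- *That a subject who revokes authorization gets more safety follow-up.* Section 10.1 says "attempts will be made to obtain permission to collect at least vital status". That is a request concerning vital status, not adverse event follow-up.

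**Conclusion.** The contradiction is real and must be resolved before the plan can be followed as written. It rests on the text alone, and is sharpest for serious events because of the mandatory wording in 9.2. It applies to dosed subjects withdrawn with an event still open. For them, the later course and resolution of that event are at risk, as is any new event after withdrawal. How many of the planned 20 subjects this would affect cannot be estimated from the documents.

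A reader might go on to conclude that the reported adverse event profile would look milder than the truth. The documents do not show this for the events that trigger withdrawal, which should be recorded beforehand. They support the narrower statement that outcome information could be incomplete and later events unseen. The point concerns safety data only, not who enters the efficacy analysis.

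**What to change.** Reconcile the sections by amending 5.4.1 and 5.4.2. After the existing restrictions, add a sentence to this effect: *These restrictions do not apply to the adverse event follow-up described in Sections 9.1 and 9.2 for subjects who have received study drug, unless the subject declines further contact.* State in the same amendment whether new events arising after withdrawal but within the study period are to be recorded, since 9.2 implies that they are. Align the consent wording so that subjects know they may be contacted about an open event after leaving and may refuse.

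This creates no new follow-up duty, because it makes room for one that 9.1 and 9.2 already impose. It changes no dose, visit or treatment rule. The cost is a short amendment with matching consent text, and a few phone calls if such cases arise.
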